#### **4. STUDY RATIONALE**

Patients who had received rituximab are at high risk of non-response to SARS-CoV-2 vaccination. It is unclear whether patients who did not develop humoral immunity after a standard protocol application with a mRNA vaccine would benefit from a second boost of mRNA SARS-CoV-2 or from a single additional shot of vector SARS-CoV-2 vaccine.

#### **5. STUDY OBJECTIVES**

SARS-CoV-2 VAC3 study

EudraCT 2021-002348-57

Version 4.0, 10. August 2021

The study aims to investigate the humoral and cellular immune responses after a second boost vaccination against SARS-CoV-2 in adult patients treated with rituximab (anti B cell therapy) who did not show response to the first two vaccinations with an mRNA vaccine.

### 5.1. Primary Objective (Hypothesis)

To assess the immunogenicity to a third vaccination mRNA-SARS-CoV-2 vaccine (Biontech/Pfizer or Moderna) compared to a vector SARS-CoV-2 (AstraZeneca) vaccination as a second boost in patients with rituximab by measuring quantitative antibody levels by enzyme-linked immunosorbent assay test (ELISA) and neutralization test (NT) or pseudo viral neutralization assay.

#### Null and alternative hypotheses:

H0: There is no statistical difference in the seroconversion rate between patients receiving a third mRNA vaccination and the patients receiving a second boost with AstraZeneca.

H1: There is statistical difference in the seroconversion rate between patients receiving a third mRNA vaccination and the patients receiving a second boost with AstraZeneca.

#### Secondary Objectives

- To compare cellular immunogenicity of the third mRNA SARS-Cov-2 vaccination will be compared to patients receiving AstraZeneca vaccination as second boost in immunosuppressed patients. T cell proliferation will be assessed, and T-cell cytokine expression will be measured using flow-cytometry following *in vitro* stimulation of peripheral blood mononuclear cells (PBMCs) with SARS-Cov-2 specific antigens.
- To assess safety of a second boost vaccination.
- To evaluate the influence of vaccination on underlying disease activity.

## 6. STUDY DESIGN

[figure not shown]
A prospective single blind randomized controlled study will be performed. A total of 68 patients with B-cell depleting therapy (rituximab) will be enrolled in this clinical trial. Four study visits per patient will be planned.

SARS-CoV-2 VAC3 study

EudraCT 2021-002348-57

Version 4.0, 10. August 2021

After inclusion of the patients (after receiving their written informed consent) serum samples for determination of antibody levels will be obtained at least 4 weeks after the second mRNA vaccination (screening visit). All patients without detectable humoral immunity against SARS-Cov2 will be invited for a second boost vaccination within 4 weeks after the screening visit. Additional study visits are scheduled at baseline (vaccination), and at weeks 1 and 4 for assessment of humoral and cellular immunity, as well as clinical signs of adverse effects of disease activity reactivation. Patients without humoral response at week 4 will be offered participation in an extended follow-up for additional 8 weeks (i.e. at week 8 and 12 after baseline)

### 6.1. Study population

Adult Patient ( $\geq 18$  years) under current rituximab therapy who did not develop humoral response against SARS-CoV-2 after their standard vaccination with Biontech/Pfizer or Moderna will be recruited at the Division of Rheumatology, Medical University of Vienna. Study entry is defined as the date of signature of the study participant (subject) on the informed consent form. All subjects enrolled will be assigned a subject code, consisting of a consecutive subject number (2 digits).

### 6.2. Inclusion criteria

Male and female subjects will be eligible for participation in this study if they:

SARS-CoV-2 VAC3 study

EudraCT 2021-002348-57

Version 4.0, 10. August 2021

22. Are  $\geq 18$  years on the day of screening
23. Have a chronic condition and have been treated with a B-cell depleting therapy (rituximab) within the last 12 months
24. Received two doses of mRNA SARS-CoV-2 (Biontech/Pfizer or Moderna) vaccine according to recommendations in the label and/or national guidelines.
25. Did not develop humoral immunity 4 weeks after second mRNA vaccination to SARS-CoV-2 (analyzed during the study “Characterization of immune responsiveness after mRNA SARS-CoV-2 Vaccination in patients with immunodeficiency or immunosuppressive therapy”, EK-Nr. 1073/2021, EudraCT Nr. 2021-000291-11)
26. A maximum of 6 months after second vaccination
27. Have an understanding of the study, agree to its provisions, and give written informed consent before study entry
28. If female and capable of bearing children – have a negative urine pregnancy test result at study entry and agree to employ adequate birth control measures for the duration of the study

### 6.3. Exclusion criteria

Subjects will be excluded from participation in this study if they:

19. Have shown humoral response to the SARS-CoV-2 vaccination
20. Had grade 3 adverse effects from the mRNA vaccination reported
21. Pregnancy and breast feeding
22. Signs of SARS-CoV-2 infection (including previous positive PCR testing)
23. Any other contraindication to any of the study compounds
24. Urgent need for next rituximab application

### 6.4. Study duration

For the individual study participant, the active blinded study phase will be 4 weeks, with possibility to enroll in an open label extension for additional 8 weeks.

### 6.5. Randomization Procedure

SARS-CoV-2 VAC3 study

EudraCT 2021-002348-57

Version 4.0, 10. August 2021

The web-based computerized randomization algorithm “Randomizer for Clinical Trials” by the Medical University of Vienna will be used for randomization. Patients will be randomized in a 1:1 ratio between the third dose mRNA SARS-CoV-2 boost (Biontech/Pfizer or Moderna, respective of their initial vaccination compound) and a single dose boost vector SARS-CoV-2 vaccine (AstraZeneca). Randomization will be stratified by presence or absence of B-cell depletion (determined at screening visit).

### **6.6.1. Blinding**

All patients will be blinded. Blinding of initial treatment allocation will be maintained throughout the 4 week study period. Blinding is ensured during the routine vaccination protocol at the General Hospital Vienna, where patients will see the pre-arranged dose aliquots in syringes without reference to the type of vaccine. To facilitate the process of vaccination of full vials, patients randomized to the same vaccine will be scheduled on the same day. Blinding will be mainly performed to prevent selective drop-outs due to knowledge of treatment allocation.

### **6.6.2. Unblinding Process**

The blinding can be lifted at the request of an investigator, when knowledge of the treatment is essential for appropriate patient management (e.g. after trial termination). In case of an emergency, the principal investigator has the sole responsibility for determining if unblinding of a patient’s treatment assignment is warranted.

If any serious adverse event arises during the study and unblinding appears necessary, the subinvestigator will notify the principal Investigator within two days in maximum. In the following the matter will be discussed and may lead to unblinding.

### **6.7.1 Withdrawal and replacement of subjects**

Criteria for withdrawal:

Subjects may prematurely discontinue from the study at any time. The study's premature discontinuation is to be understood when the subject did not undergo complete the last visit (study visit 4) or all pivotal assessments during the study.

Subjects must be withdrawn under the following circumstances:

SARS-CoV-2 VAC3 study

EudraCT 2021-002348-57

Version 4.0, 10. August 2021

- at their own request
- if the investigator feels it would not be in the best interest of the subject to continue
- if the subject violates conditions laid out in the consent form/information sheet or disregards instructions by the study personal

In all cases, the reason why subjects are withdrawn must be recorded in detail in the CRF and the subject's medical records. Should the study be discontinued prematurely, all study materials (complete, partially completed, and empty CRFs) will be retained.

Follow-up of patients withdrawn from the study:

In case of premature discontinuation after the start of vaccination, no further investigations concerning the study will be performed. Furthermore, participants may request that no more data will be recorded from the time point of withdrawal and that all biological samples collected in the course of the study will be destroyed.

### 6.7.2 Premature termination of the study

The sponsor has the right to close this study at any time. The IEC and the competent regulatory authority must be informed within 15 days of early termination.

The trial or single-dose steps will be terminated prematurely in the following cases:

- If the number of drop-outs is so high that proper completion of the trial cannot realistically be expected.
- Recruitment is not reaching the critical number

## 9.8. Adverse events and reporting

### bb. Definition of adverse events

An adverse event is any untoward medical occurrence in a patient or clinical investigation subject administered a pharmaceutical product and which does not necessarily have a causal relationship with this treatment. An adverse event (AE) can therefore be any unfavourable and unintended sign (including an abnormal laboratory finding), symptom, or disease temporally associated with the use of a medicinal (investigational) product, whether or not related to the medicinal (investigational) product (see the ICH Guideline for Clinical Safety Data Management: Definitions and Standards for Expedited Reporting)

Adverse events include:

SARS-CoV-2 VAC3 study

EudraCT 2021-002348-57

Version 4.0, 10. August 2021

- Exacerbation of a pre-existing disease.
- Increase in frequency or intensity of a pre-existing episodic disease or medical condition.
- Disease or medical condition detected or diagnosed after study drug administration even though it may have been present prior to the start of the study.
- Continuous persistent disease or symptoms present at baseline that worsen following the start of the study.
- Lack of efficacy in the acute treatment of a life-threatening disease.
- Events considered by the Investigator to be related to study-mandated procedures.
- Abnormal assessments, e.g., ECG and physical examination findings, must be reported as AEs if they represent a clinically significant finding that was not present at baseline or worsened during the course of the study.
- Laboratory test abnormalities must be reported as AEs if they represent a clinically significant finding, symptomatic or not, which was not present at baseline or worsened during the course of the study or led to dose reduction, interruption or permanent discontinuation of study drug.

Adverse events do not include:

- Pre-planned interventions or occurrence of endpoints specified in the study protocol are not considered AE's, if not defined otherwise (eg.as a result of overdose)
- Medical or surgical procedure, e.g., surgery, endoscopy, tooth extraction, transfusion. However, the event leading to the procedure is an AE. If this event is serious, the procedure must be described in the SAE narrative.
- Pre-existing disease or medical condition that does not worsen.
- Situations in which an adverse change did not occur, e.g., hospitalisations for cosmetic elective surgery or for social and/or convenience reasons.

Overdose of either study drug or concomitant medication without any signs or symptoms.

However, overdose must be mentioned in the Study Drug Log.

SARS-CoV-2 VAC3 study

EudraCT 2021-002348-57

Version 4.0, 10. August 2021

cc. Definition of serious adverse events (SAEs)

A Serious Adverse Event (SAE) is defined by the International Conference on Harmonization (ICH) guidelines as any AE fulfilling at least one of the following criteria:

- Fatal (including fetal death).
- Life-threatening – defined as an event in which the subject was, in the judgment of the investigator, at risk of death at the time of the event; it does not refer to an event that hypothetically might have caused death had it been more severe.
- Requiring subject's hospitalization or prolongation of existing hospitalization – inpatient hospitalization refers to any inpatient admission, regardless of length of stay.
- Resulting in persistent or significant disability or incapacity (i.e., a substantial disruption of a person's ability to conduct normal life functions).
- Congenital anomaly or birth defect.
- Is medically significant or requires intervention to prevent at least one of the outcomes listed above.

In case of any SAE, the investigator has to use all means to ensure patient's safety. Every SAE has to be reported as outlined in section 16.8.

dd. Definition of suspected or unexpected serious adverse reactions (SUSARs)

SUSARs are all suspected adverse reactions related to the study drug that are both unexpected (not previously described in the SmPC or Investigator's brochure) and serious.

ee. Pregnancy

Maternal pregnancies must be reported to the principal investigator/sponsor. To ensure subject safety, each pregnancy must be reported to the PI/sponsor within 2 weeks of learning of its occurrence.

Pregnancies, should be followed up and reported to the PI/sponsor until the outcome of the pregnancy (including premature termination) and status of mother and child is known.

ff. Severity of adverse events

The severity of clinical AEs is graded on a three-point scale: mild, moderate, severe, and

SARS-CoV-2 VAC3 study

EudraCT 2021-002348-57

Version 4.0, 10. August 2021

reported on specific AE pages of the CRF.

If the severity of an AE worsens during study drug administration, only the worst intensity should be reported on the AE page. If the AE lessens in intensity, no change in the severity is required:

- *Mild* - Event may be noticeable to subject; does not influence daily activities; the AE resolves spontaneously or may require minimal therapeutic intervention;
- *Moderate* - Event may make subject uncomfortable; performance of daily activities may be influenced; intervention may be needed; the AE produces no sequelae.
- *Severe* - Event may cause noticeable discomfort; usually interferes with daily activities; subject may not be able to continue in the study; the AE produces sequelae, which require prolonged therapeutic intervention.

A mild, moderate or severe AE may or may not be serious.

#### gg. Relationship of adverse events to study drug

For all AEs, the investigator will assess the causal relationship between the study drug and the AE using his/her clinical expertise and judgment according to the following algorithm that best fits the circumstances of the AE:

#### **Not related**

- May or may not follow a temporal sequence from administration of the study product
- Is biologically implausible and does not follow known response pattern to the suspect study drug (if response pattern is previously known).
- Can be explained by the known characteristics of the subject's clinical state or other modes of therapy administered to the subject.

#### **Unlikely**

- There is a reasonable temporal relation between the AE and the intake of the study medication, but there is a plausible other explanation for the occurrence of the AE.

#### **Possibly**

- The AE has a reasonable temporal relationship with drug administration.

SARS-CoV-2 VAC3 study

EudraCT 2021-002348-57

Version 4.0, 10. August 2021

- The AE may equally be explained by the study subject's clinically state, environmental or toxic factors, or concomitant therapy administered to the study subject.
- The relationship between study drug and AE may also be pharmacologically or clinically plausible.

**Probably**

- There is a reasonable temporal relation between the AE and the intake of the study medication, and plausible reasons point to a causal relation with the study medication.

**Related**

- Reasonable temporal relation between the AE and the intake of the study medication and
- There is no other explanation for the AE and
- Subsidence or disappearance of the AE on withdrawal of the study medication and
- Recurrence of the symptoms on restart at previous dose (only applies for re-institution of medication).

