**hh. Adverse events reporting procedures**

A special section is designated to adverse events in the case report form. For each subject, adverse events occurring after signing the informed consent must be recorded on the applicable adverse events page(s) in the case report form. Recording should be done in a concise manner using standard, acceptable medical terms. The adverse event recorded should not be a procedure or a clinical measurement (i.e., a laboratory value or vital sign) but should reflect the reason for the procedure or the diagnosis based on the abnormal measurement. If, in the investigator's judgment, a clinically significant worsening from baseline is observed in laboratory or other parameters, physical exam finding, or vital sign, a corresponding clinical adverse event should be recorded on the adverse event page(s) of the CRF. If a specific medical diagnosis has been made that diagnosis should be recorded on the adverse event page(s) of the CRF.

SARS-CoV-2 VAC3 study

EudraCT 2021-002348-57

Version 4.0, 10. August 2021

SAEs and any newly identified pregnancy (maternal or paternal exposure), malignancy, overdose, opportunistic infection or case of active TB occurring after first administration of study agent in subjects participating in this clinical trial requires submission of a Safety Report Form to the Sponsor (only if other sites are reporting SAE) within 24 hours of notification or observation.

*The following details must thereby be entered:*

- Type of adverse event
- Start (date and time)
- End (date and time)
- Severity (mild, moderate, severe)
- Serious (no / yes)
- Unexpected (no / yes)
- Outcome (resolved, ongoing, ongoing – improved, ongoing – worsening)
- Relation to study drug (unrelated, possibly related, definitely related)

Adverse events are to be documented in the case report form in accordance with the above mentioned criteria.

ii. Reporting procedures for SAEs

In the event of serious, the investigator has to use all supportive measures for best patient treatment. A serious adverse event must be reported if it occurs during a subject's participation in the study (whether receiving study agent or not) or within six (6) months of receiving the last dose of study agent.

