## 10. METHODOLOGY

### 7.1 Study design and blood samples

A randomized controlled single-blind phase II trial will be performed. A total of 68 patients with current rituximab therapy who did not develop humoral immune response to SARS-CoV-2 after vaccination with mRNA SARS-CoV-2 vaccine (Biontech/Pfizer or Moderna). Four study visits per patient will be planned during the course of the trial: screening visit (-0-14 days), baseline, week 1, week 4. Patients will be unblinded at week 4. In addition, patients who did not show humoral response at week 4 will be invited for two additional study visits at week 8 and week 12 in an open label approach. Vaccination will take place at baseline visit.

Blood samples for the determination of SARS-CoV-2 antibodies will be obtained at screening visit, at week 1, week 4 and during the potential extension of the study at week 8 and week 12.

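### The six-level causality algorithm includes a withdrawal criterion that cannot literally apply to one injection, and it does not map to the three-level entry list

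*Supplement*

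**What the plan says.** All references are to protocol version 4.0.

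- **Product.** Section 6.5 randomises patients to a "third dose mRNA SARS-CoV-2 boost" or to "a single dose boost vector SARS-CoV-2 vaccine (AstraZeneca"). Section 7.1 adds: "Vaccination will take place at baseline visit". Each patient therefore gets one study administration.
- **How causality is assessed.** Section 9.8 gg has the investigator grade every adverse event "using his/her clinical expertise and judgment according to the following algorithm that best fits the circumstances of the AE". Six categories follow: *Not related*, *Unlikely*, *Possibly*, *Probably*, *Related*, *Not assessable*.
- ***Related*.** There are four conditions joined by 'and': timing, absence of another explanation, "Subsidence or disappearance of the AE on withdrawal of the study medication and" recurrence on restart. Only the recurrence condition is limited, to cases where the medication is given again.
- ***Probably* and *Possibly*.** *Probably* needs reasonable timing and that "plausible reasons point to a causal relation with the study medication". *Possibly* includes the statement "The AE may equally be explained by the study" patient's clinical state, environmental or toxic factors, or other therapy.
- **What is entered.** Section 9.8 hh lists the details to be entered for an event, among them "Relation to study drug (unrelated, possibly related, definitely related"), and then ties this list to the case report form.
- **Use.** Safety of the boost is a secondary objective (section 5) and a secondary endpoint (section 7.3.2). Section 9.3 plans descriptive statistics for it.

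**The concern.** There are two faults, and each makes the other worse.

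The first is a criterion written for continuing medication and applied to a product given once. Subsidence on withdrawal is informative when a drug can be stopped. After a single injection it has no literal meaning, yet *Related* requires it.

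The second is that assessment and recording use different scales. Had *Probably* been available for entry, the first fault would matter little, because a clear injection reaction could be recorded there. It has no entry of its own, so the investigator must move such an event up to 'definitely related' or down to 'possibly related'. The downward move places it with events that the protocol describes as equally explained by something else.

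The consistency of the causality grade is what is at stake. Two investigators who agree about an event can record it differently and both be following the protocol. Section 6.6.1 states blinding for patients only. If investigators know which vaccine was given, an assumption that the protocol neither confirms nor excludes, an unregulated choice of this kind could also be influenced by that knowledge.

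**Working it through.** The plan states no figure on this point and no statistical calculation applies. The check sets the two scales side by side and then tests each condition of *Related* against a one-dose design.

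**Step 1: match the scales.** Pairing is by nearest wording, since the protocol gives no mapping.

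| Category defined in 9.8 gg | Entry listed in 9.8 hh |
|---|---|
| *Not related* | unrelated |
| *Unlikely* | none |
| *Possibly* | possibly related |
| *Probably* | none |
| *Related* | definitely related (presumed) |
| *Not assessable* | none |

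Six categories less three entries leaves 6 − 3 = 3 without a counterpart. The count does not depend on the pairing chosen, because three entries can correspond one-to-one with at most three categories. Which three are left over does depend on it; by wording they are *Unlikely*, *Probably* and *Not assessable*.

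**Step 2: test the four conditions of *Related* after one vaccination at baseline.**

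1. Reasonable timing: can be met.
2. No other explanation: can be met.
3. Subsidence on withdrawal: no ongoing medication exists to withdraw, and no exemption is written. It cannot be met literally.
4. Recurrence on restart: waived by its own wording, as the product is not given again.

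Two conditions can be met, one is waived, and one has no literal meaning. Because the conditions are joined by 'and', the third is enough to prevent a literal classification as *Related*.

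**Step 3: follow one event through.** Take an injection-site reaction with plausible timing and no other explanation.

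- Conditions 1 and 2 hold and condition 3 does not, so on a literal reading it is not *Related*.
- It fits *Probably*: the timing is reasonable and the reasons point to the vaccine.
- *Probably* has no entry in hh. The investigator enters either 'possibly related' or 'definitely related', and nothing in the protocol says which.

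An event judged *Unlikely* or *Not assessable* meets the same difficulty, again without a rule.

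**The case against.** The strongest reply is that gg asks for a best fit by clinical judgment and does not set a mechanical gate. An investigator may treat spontaneous resolution as subsidence and choose *Related*. The other five categories need no withdrawal, and recurrence is already waived. Nothing equates 'definitely related' in hh with *Related* in gg, so an investigator may enter 'definitely related' without meeting the four conditions. This stands, and it limits the point. A reader might infer that no reaction can ever be classed as related, or that all reactions collapse into 'possibly related'. The documents do not support either inference, since both need the strictest reading of gg together with a mapping that the protocol never states.

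A reader might also infer that SUSAR reporting is impaired. It is not blocked. Section 9.8 jj sends all serious adverse events to the sponsor for evaluation, and its threshold is a reasonable suspicion of causality, with which a 'possibly related' entry is compatible.

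Two further limits are fair. No table by causality grade is planned, and counts, severity and seriousness by arm do not use the grade. The case report form itself is not shown. The three-level list is the protocol's description of what must be entered, and it follows a sentence about the Safety Report Form, although the closing line of hh ties it to the case report form.

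The reply does not remove the mismatch. Judgment can work around both faults, but different investigators may do so differently, and that is the inconsistency at issue.

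**Conclusion.** The point holds as an inconsistency in the safety wording. *Related* contains one condition, without exemption, that cannot literally apply to a single vaccination. Three of the six defined categories have no counterpart in the entry list and no mapping. On the literal reading, a clear vaccine reaction misses *Related*, and one judged *Probably* is entered as 'possibly' or 'definitely' related at the investigator's discretion.

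The effect is confined to the consistency of causality coding behind a descriptive secondary endpoint. How many events would be coded differently cannot be derived from the documents, and understatement of vaccine causality is a risk, not a certainty. The primary analysis is unaffected.

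The conclusion assumes that hh describes the entries actually offered on the case report form, and that categories and entries pair by nearest wording. If the form carries all six levels, the recording fault disappears in practice and only the protocol text needs correction. The withdrawal criterion would still need attention.

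**What to change.** 1. In section 9.8 gg, remove the withdrawal condition from *Related*, or state that it does not apply to a product given once. The recurrence condition can stay, as it already has its exemption.
2. In section 9.8 hh, make the entry list identical to the six categories. Alternatively, keep three entries and state which entry each of the six categories takes, including *Unlikely*, *Probably* and *Not assessable*.
3. State which levels count as related in the safety summaries.
4. Re-code any events already entered, once, under the aligned scale.

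The cost is a few lines of protocol wording, one entry list if it differs, and a single pass over recorded events in a trial of 68 planned patients. Sample size, visits and the primary analysis do not change.
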